As a result of both the successes of the Phase II and Phase III collaborations, and the shortcomings of the Phase I 1308 collaboration, the RETAIN team decided to end our collaboration with 1308 and focus all resources squarely on the Phase II and Phase III collaborations. This decision was discussed with the 1308 investigators on November 27 and the RETAIN team received approval to move forward exclusively focused on Phases II and II from the sponsor, the Nation Cancer Institute, on November 30, 2017.

As a result of this change, the team removed RTOG 1308-relevant language from the IRB protocol and ended Penn's oversight of the RETAIN trial at MDACC, a relying institution. The MGH and Washington University research teams closed out the RETAIN study at their respective sites.

7. Approved January 25, 2018

a. Phase II – Modification to BASC screening procedures

The study teams for BASC and RETAIN implemented a RETAIN-related change to the phone screen script being used at Northwestern and Penn. For patients randomized to RETAIN, the team stopped asking, "Does this sound like something that you are interested in?" before administering the RETAIN surveys. They simply transitioned from introducing the study basics to administering the RETAIN questions by saying, "Now we ask that you answer a few more questions before finalizing the details of your intake visit."

The goal of this change was to provide an opportunity to capture RETAIN baseline data that was not being collected systematically due to early withdraws from the phone screen call.

b. Phases II and III - Revisions to the Compared Riskiness Scale

The study team examined the phrasing for the Compared Riskiness scale in an Amazon mechanical Turk study aimed at countering floor effects in our measure of risk perception. As a result of this investigation we made several changes to the phrasing of the questions in the scale. We did not add new items to the scale.

8. Approved February 21, 2018

a. Phase II – Modification to MOVE IT recruitment procedures

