Participants will be randomized to the 3 experimental arms (low-, middle-, and high-level incentive) in equal, 33.3% probabilities. A Penn analyst will implement block randomization stratified by site in the BASC parent trial and stratified by clinical research coordinator in the MOVE IT trial. The trial's primary statistician on the Penn research staff will provide a block randomization scheme for each clinical research coordinator (MOVE IT) and will upload a CSV file to the REDCap randomization module. He/she will also provide a block randomization scheme for each site for the Access Data Management System (BASC) (see Section 10.a.1. Data Management – BASC). The parent trial research staff will respond to initial eligibility prompts n the REDCap software through an initialization step and will immediately receive the randomization assignment for that participant. Randomization will take place in the DMS for the BASC trial. This will allow them to message to the participant the appropriate incentive level for participation in the parent trial, and present the correct paper consent based on their arm assignment (see Sections 8.g. Parent Trial Informed Consent).

i. BASC

Randomization and group assignment occurs after pre-screening data are collected and RETAIN eligibility probes are administered on the eligibility pre-screening call for the BASC parent trial (see Section 8.e.2 Administration of Survey Instruments – BASC). Research staff will know group assignment when patients are first introduced to the BASC trial on the phone in order to message the assigned payment (\$0, \$200, \$500) for the participant. Participants who are deemed preliminarily eligible will schedule an intake session, where they will view the electronic BASC parent trial consent form (\$0, \$200, or \$500) and receive a paper copy of the form with respective incentive information.

ii. MOVE IT

Randomization and group assignment occur after MOVE IT screening steps (see Section 8.e.3 Administration of Survey Instruments – MOVE IT) following clinical research coordinators' brief introduction to the study upon entering patients' hospital room. Clinical research coordinators will randomize patients and know the group assignment as they complete the recruitment script and assess patients' interest in learning about the MOVE IT trial. Assignment occurs prior to registering the patient in the Way to Health platform used for survey administration.

8. Study Procedures

a. Screening

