Using a recruitment script in REDCap, clinical research coordinators will describe a study that aims to help patients improve their mobility and prevent them from needing to return to the hospital. The REDCap-hosted MOVE IT recruitment script will prompt the clinical research coordinator to assess for patient's eligibility in the MOVE IT study through two screening questions. Eligible patients will be randomized in real time to one of three incentives for participation (\$0, \$100, or \$300). The clinical research coordinator will finish reading the recruitment script, indicating the amount participants will be paid for the MOVE IT Trial. Ineligible patients will not be randomized or enrolled on the RETAIN trial.

For patients who are interested in learning more about the MOVE IT study, the MOVE IT clinical research coordinators will proceed to register the participant in the Way to Health platform and administer the tools in Way to Health via tablet (see Section 10.a.3. Data Management- MOVE IT). The patient will be asked to complete several short questionnaires: 1) demographics, 2) personal financial well-being, 2) attitudes towards biomedical research, and 3) prior experience in research.

Once the patient has completed aforementioned tools in Way to Health, the clinical research coordinator will return to the REDCap database and read a pre-consent introduction script before presenting the an electronic image of the MOVE IT informed consent/ HIPAA forms with additional information regarding the RETAIN incentive randomization condition. By presenting the MOVE IT consent with randomized compensation information electronically, we will assess the amount of time

participants spend reading each part of the main trial consent form. Each section will be presented as a survey in REDCap. Time-stamp data collected for this REDCap module will be linked by the study ID generated in Way to Health.

Once participants finish reading and before signing a paper version of the MOVE IT trial paper consent, they will complete brief assessments of perceptions of research risk. They will also complete assessments on perceptions of the difference between research and individualized patient care and understanding of the MOVE IT via a trial elements quiz. All of these measures will be administered via the Way to Health platform on a tablet. The responses to the quiz will be reviewed with participants, during which participants' questions will be answered.

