Analyses of interaction terms will be structured as tests of non-inferiority. The null hypothesis, for both trials, will be that the use of incentives meets criteria for undue or unjust inducement. We can reject the null, and conclude the absence of undue or unjust inducement, if the interaction terms are "small" according to pre-specified criteria (in technical terms, the inferiority margin). Said a different way, our analyses are designed to determine if we can exclude the possibility that incentives represent undue or unjust inducements if the resulting interaction terms are sufficiently small. Specifically, we will use one-sided alpha levels of 0.05 to exclude, with 95% confidence, the possibility that any of these interaction odds ratios are >2.0.

We will explore temporal trends in incentives' effects over the study period using stratified analyses. If temporal trends are noted, as may occur if prospective patients learn of the incentives used in these studies, we will adjust for their influence by entering time as a covariate, modeled as a spline. We will evaluate potential effect modifiers (variables in Table 1) using stratified analyses. If differences among strata appear, we will formally test their corresponding interactions with the incentive amount.

Patient level covariates	Variable coding or definition		
• Age	Continuous		
• Gender	Binary		
Race	Categorical		
Marital status	Categorical		
Education	Categorical		
Income	Categorical		
Economic well-being	Categorical		
Prior research participation	Categorical		
Attitudes towards research:	Continuous, measured using the Research Attitudes Questionnaire-7 (RAQ-7).		

TABLE 1 FACTORS FOR ADJUSTMENT AND EXPLORATION OF EFFECT MODIFICATION
Potential factors for adjustment

6. Approach to missing data & sensitivity analyses

In addition to introducing several modifications to enrollment procedures to safeguard against missing data, some guidelines have been implemented to address missing data. The study team is particularly concerned about missingness of key RETAIN outcomes due to post-randomization ineligibility (i.e. a patient is discovered to be ineligible for the parent trial after randomization into RETAIN). If missingness due to parent trial ineligibility does not exceed 10%, the primary analysis will be limited to participants with complete data.

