The primary outcome is the proportion of participants assigned to each incentive amount that consent to enroll in each of the two parent RCTs.

b. Primary analytic sample

Intention-to-treat (ITT) approach such that the analytic sample will include all patients randomized in the RETAIN trial, even if ultimately deemed ineligible for the parent trials.

c. Primary analysis

We will first assess bivariate relationships of incentives with the primary outcome using chi-square tests for comparisons of proportions. To examine the hypothesized statistical interactions, we will use logistic, linear, or quantile regression, as appropriate based on outcome parameterizations and distributions. In the above analyses we treated incentive as an ordered variable. In all analyses in which the parent trial enrolls in multiple centers, we will model the center from which patients are recruited as a fixed effect, thereby mitigating confounding by center and adjusting variance estimates for clustering of participants within centers. To adjust for chance covariate imbalance among arms, primary analyses will include covariates (see Table 1) in multivariable models if they are significantly associated with the intervention arm and predictive of enrollment in the parent trials in bivariate analyses. To avoid problems in estimating odds ratios due to sparse data, we will limit the number of covariates to no more than 1 per 10 participants enrolling in the parent trials. In all analyses related to the BASC parent trial, we will model the center from which patients are recruited as a fixed effect, thereby mitigating confounding by centers are recruited as a fixed effect, thereby mitigating confounding by center and adjust related to the BASC parent trial, we will model the center from which patients are recruited as a fixed effect, thereby mitigating confounding by center and adjusting variance estimates for clustering of participants within centers.

Our analyses to rule out undue and unjust inducements entail three primary covariates: risk perception, annual household income, and economic well-being. All models will use enrollment in the parent trial as the outcome. To determine if incentives represent undue inducements for research participation, we will test the statistical interaction between incentive size and the primary covariate of risk perception on

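### In the current MOVE IT text the inducement moderators are collected after the offer and after an interest question, and the Final SAP has no rule for early decliners who lack them.

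*Combined protocol and SAP*

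**What the plan says.** **Order of events.** Final Protocol section 7.b.ii (Assignment, MOVE IT) says coordinators "know the group assignment as they complete the recruitment script and assess patients' interest in learning about the MOVE IT trial". It adds: "Assignment occurs prior to registering the patient in the Way to Health platform used for survey administration". Under section 8.d.ii (Administration of Survey Instruments, MOVE IT) the amount is stated in the recruitment script. Registration and the questionnaires on demographics, personal financial well-being, research attitudes and research experience then apply to a subset: "For patients who are interested in learning more about the MOVE IT study". Risk perception comes later still, once the electronic consent has been read: "before signing a paper version of the MOVE IT trial paper consent, they will complete brief assessments of perceptions of research risk". The MOVE IT calendar (section 9.ii) agrees, listing the Compared Riskiness Scale once, after consent administration. The BASC calendar lists it both before and after.

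**Change log.** The entry approved April 23, 2018 says that demographic data could be obtained on MOVE IT decliners but risk data on early decliners could not. The scale was therefore added to the baseline surveys, with a short account of risks and benefits early in the script. For BASC, the entry approved January 25, 2018 removed the interest question ahead of the surveys: "They simply transitioned from introducing the study basics to administering the RETAIN questions". No matching MOVE IT change is logged.

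**Analysis.** Final SAP section 5.b says that "the analytic sample will include all patients randomized in the RETAIN trial". Section 5.c fits three models for enrolment, each with an interaction between incentive and one moderator: risk perception, household income or economic well-being. Inducement is excluded if the interaction odds ratio is shown to be below 2.0 at one-sided 0.05. Nothing is said about patients whose moderator is missing. The propensity weighting in section 6.c covers secondary outcomes.

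**The concern.** A patient who hears the amount and says no has a known outcome, not enrolled, but may have no moderator value. Standard logistic software omits such a patient. The fitted model then describes patients who stayed interested after the offer, and staying interested is itself a response to the offer.

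Dropping patients by arm and decision alone would leave the interaction odds ratio unchanged. It changes when, among non-enrolled patients in an arm, the chance of having a moderator value depends on the moderator. That happens if a larger offer draws low-income patients past the interest question more than others, which is the behaviour the unjust-inducement test is meant to detect.

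At stake is the primary aim and the basis of the sample size: a claim that inducement is absent. The interim stopping rules use the same three interactions, so they would share any blind spot.

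**Working it through.** **1. The plan's own figure.** Final SAP section 7.b states at least 80% power with 96 patients per cell, 50% enrolment, true odds ratio 1, margin 2.0 and one-sided alpha 0.0427 (z = 1.720). Power = Φ(ln 2/SE − z), with SE² = Σ 1/[n p(1−p)] over cells.
- Two cells (the $0-arm odds ratio fixed at 1): SE² = 2/(96 × 0.25) = 0.0833, SE = 0.289, power 75.2%.
- Four cells (ratio of odds ratios): SE² = 0.1667, SE = 0.408, power 49.1%.

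Neither gives 80%. That is a separate matter; the formula and cell size are used below.

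**2. Inducement acting at the interest step.** Assumed, not from the documents: top versus bottom arm, binary income, 96 per cell. Interest is 50% in every cell except 75% for low-income patients offered the top amount. Of the interested, 80% consent in every cell. The test is one-sided 0.05 (z = 1.645) against 2.0.
- All randomised: enrolment is 0.5 × 0.8 = 0.40 in three cells and 0.75 × 0.8 = 0.60 in the fourth. Interaction odds ratio = (0.60/0.40)/(0.40/0.60) = 2.25.
- Interested only: 0.80 in every cell, so the odds ratio is 1.0.
- Dropped: 1 − (0.50 + 0.50 + 0.50 + 0.75)/4 = 44%.
- Chance of declaring absence, all randomised: SE² = 4/(96 × 0.24) = 0.1736, SE = 0.417; Φ[(ln 2 − ln 2.25)/0.417 − 1.645] = Φ(−1.93) = 2.7%.
- Chance of declaring absence, interested only: SE² = 3/(48 × 0.16) + 1/(72 × 0.16) = 0.4774, SE = 0.691; Φ[ln 2/0.691 − 1.645] = Φ(−0.64) = 26%.

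The mechanism shows among top-arm non-enrolled patients. A moderator value exists for 0.15/0.40 = 37.5% of those with low income and 0.10/0.60 = 16.7% of those with high income. The ratio, 2.25, cancels the true interaction exactly.

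**3. Range.** Same structure, true odds ratio 2.0, alpha 0.0427, consent among the interested 60–90%, overall early decline 23–45%. The chance of wrongly ruling out inducement is 4.3% with all randomised and about 17–39% with the interested only.

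**4. Inducement acting at consent.** Assumed: interest is 60% in every cell; consent among the interested is 50%, except 75% for low-income patients in the top arm.
- All randomised: (0.45/0.55)/(0.30/0.70) = 1.91.
- Interested only: (0.75/0.25)/(0.50/0.50) = 3.0.
- Chance of declaring absence at 0.05, all randomised: SE² = 3/(96 × 0.21) + 1/(96 × 0.2475) = 0.1909, SE = 0.437; Φ[(ln 2 − ln 1.91)/0.437 − 1.645] = about 6%.
- Chance of declaring absence at 0.05, interested only (57.6 per cell): SE² = 3/(57.6 × 0.25) + 1/(57.6 × 0.1875) = 0.3009, SE = 0.549; Φ[(ln 2 − ln 3)/0.549 − 1.645] = about 1%.

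Here the bias makes the absence claim harder to reach.

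**5. Precision when there is no inducement.** Keep overall consent at 50% and drop 40% before the surveys. Then 346 of 576 remain (57.6 per cell) and consent among them is 0.50/0.60 = 83.3%. Four-cell SE² = 4/(57.6 × 0.833 × 0.167) = 0.50, and power at 0.0427 falls from 49.1% to 23.0%.

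**The case against.** The sponsor saw this problem and acted on it. The April 2018 log entry names missing data among early decliners, reports a route to demographic data on them, moves the risk scale forward and puts a risk description early in the script. The November 2017 entry says MOVE IT already had a HIPAA waiver for using non-consenters' data. A reader might infer that the moderators exist only for interested patients; with that entry on record, the documents do not support so firm a statement. What the entry leaves open is whether the demographic data include income or well-being. Section 8.d.ii lists demographics and financial well-being as separate instruments, and its baseline surveys still follow the interest step. I do not treat the difference between log and protocol text as an error in itself. It leaves unclear what is held on early decliners.

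A reader might also infer that every early decliner leaves the models. The Final SAP does not say so: it claims all randomised patients and is silent on missing moderators. Complete-case loss is the likely default, not a stated rule.

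A third tempting reading is that the bias always favours the absence claim. Step 4 shows otherwise, and step 5 shows that lost patients alone make the claim harder to reach.

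A fourth is that removing the Original SAP's missing-data section opened the gap. Its 10% rule, "If missingness due to parent trial ineligibility does not exceed 10%, the primary analysis will be limited to participants with complete data", and the imputation and shifted-intercept analyses after it concerned consent outcomes of patients found ineligible after randomisation. They did not supply moderators for decliners, whose outcome is known. Its one sentence on incomplete instruments was limited to secondary analyses.

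Finally, the illustration is simplified: two arms and a binary moderator, against an ordered three-level incentive and continuous risk in the SAP, with all inducement placed at one step. That stands as a limit on the size, not on the mechanism.

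**Conclusion.** The point holds in a limited form. Under the current MOVE IT text, patients who decline on hearing the amount may lack income, well-being or risk values, and the Final SAP does not say how the three inducement models treat them. A default complete-case fit would condition on a post-offer response. If inducement acts at the interest step, a true odds ratio of 2.25 can appear as 1.0, with false exclusion rising from about 3% to 26%. If it acts at consent, the error runs the other way (1.91 to 3.0). These figures rest on assumed interest and consent rates. The documents give no early-decline rate and do not show at which step inducement would act, so neither the size nor the direction in this trial is known.

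**What to change.** **Data collection.** Reconcile Final Protocol section 8.d.ii and the MOVE IT calendar with the April 2018 log entry, and state which moderators are held for patients who decline on hearing the amount. Following the step taken in BASC, give the short income, well-being and risk items to every randomised MOVE IT patient before interest is asked. Income and well-being may be asked before the amount is stated. Keep a risk measure after the amount, because the offer's effect on perceived risk is itself a study question.

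**Final SAP section 5.** Keep early decliners in the interaction models as not enrolled. Report moderator missingness by arm and decision stage. Add a tipping-point analysis that shifts the moderator distribution of early decliners by arm, over a range fixed in advance. Qualify the absence claim if the upper bound crosses 2.0 within a plausible part of that range. Imputation alone is not enough if no moderator values are observed at that stage.

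**Cost.** A reordered script, a few survey minutes for patients who may decline, some refusals, and one extra sensitivity analysis. If recruitment is already complete, the SAP changes can still be made.
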